6.2. Secondary Analyses

Secondary analyses comprise intra-individual comparative descriptive analyses of all pathological results to assess correlation between ICC and IHC results.

7. Sample Size Calculation

According to previous experience concerning the value of ICC in lung cancer diagnosis, sensitivity/specificity of this method is expected to be lower as compared to IHC. While exact figures for PD-L1 detection (ICC and IHC) are not available we anticipate a specificity of approx. 90% of PD-L1 detection via ICC as compared to IHC. Previous application of the PD-L1 antibody used for detection in histological samples revealed a prevalence of approx. 25% in PD-L1 positive NSCLC patients (Garon et al. 2015). Buderer (1996) described a method for sample size calculation for sensitivity and specificity incorporating the prevalence of disease. We used this method and specified the required parameters as followed:

Sample size (n) was calculated according to the formula:

$$n = \frac{Z_{\alpha/2}^2 \frac{SP(1-SP)}{W^2}}{(1-P)}$$

where

$Z_{\alpha/2}$	z value from standard normal distribution with $\alpha=0.05$
SP	specified specificity (90%)
W	width of 95% confidence interval (10%)
P	prevalence of disease (25%)

This resulted in a number of 46 patients, which was amended by a drop-out rate of approx. 10% to give a total patient number of

n=50 patients

which should at least allow for a valuable qualitative assessment of the feasibility of PD-L1 diagnostic based on ICC and provide a basis for possible future studies.

8. References

1. Poole RM, Pembrolizumab: first global approval, *Drugs*. 2014 Oct;74(16):1973-81
2. Rizvi NA et al., Safety and clinical activity of MK-2475 as initial therapy in patients with advanced non-small cell lung cancer (NSCLC) [Abstract No. 8007]; 50th Annual Meeting of the American Society of Clinical Oncology.2014; Chicago, IL
3. Garon EB et al., Antitumor Activity of Pembrolizumab (Pembro; MK-3475) and Correlation With Programmed Death Ligand 1 (PD-L1) Expression in a Pooled Analysis of Patients With Advanced NSCLC ; ESMO 2014
6. Siegel R , Naishadham D , Jemal A . Cancer statistics, 2013 . *CA Cancer J Clin* . 2013 ; 63 (1) : 11 – 30
7. Garon EB et al., Pembrolizumab for the treatment of non-small-cell lung cancer. *N Engl J Med*. 2015 May 21;372(21):2018-28.

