6.1. Primary Analysis

The main hypothesis is, that ICC analysis of PD-L1 from pleural effusion has a relevant diagnostic value with a specificity of ~90% as compared to the immunohistochemical reference standard. To test this hypothesis, the number of PD-L1 positive and negative detections for each sample type will be documented and used for calculation of sensitivity and specificity. Furthermore, the frequency with 95% confidence interval of PD-L1 positive patients according to ICC of pleural fluid will be calculated.

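### The 10% precision for specificity in section 7 is not delivered on the lower side: about 34 IHC-negative patients give roughly 76% to 96%, not the implied 80% to 100%

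*Combined protocol and SAP*

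**What the plan says.** Section 7 (Sample Size Calculation) uses a published formula for specificity that allows for prevalence: n = z² × SP(1 − SP) / W², divided by (1 − P). The multiplier is the "z value from standard normal distribution with" alpha 0.05, SP is 90%, P is 25%, and W is described by the words "width of 95% confidence interval (10", that is, 10%. The outcome is stated as "This resulted in a number of 46 patients", then raised to 50 for dropout of about 10%.

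Section 6.1 (Primary Analysis) says that counts of positive and negative detections will be used to calculate sensitivity and specificity, and mentions no interval for either. The one interval it plans is for another quantity: "the frequency with 95% confidence interval of PD-L1 positive patients according to ICC of pleural fluid will be calculated". No method is given for it. No exact, score or other interval method is named anywhere in the document.

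**The concern.** The formula in section 7 is the normal-approximation (Wald) interval for a proportion, rearranged to give n. That approximation is poor when the proportion is near 1 and the group is small, and both apply here. The symmetric 10 points that the size rests on may therefore misdescribe what the trial can show.

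The error is in the favourable direction. A reader of section 7 would expect an observed specificity of 90% to exclude values below 80%. Specificity is the figure in the main hypothesis, and section 7 offers the pilot as a basis for later studies, so an optimistic lower limit could carry over into their design.

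**Working it through.** **Inputs.** From section 7: z = 1.96 (alpha 0.05, two-sided), SP = 0.90, W = 0.10, P = 0.25, 46 evaluable patients, 50 in total.

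**1. Reproduce the plan's figure.**
- IHC-negative patients needed: 1.96² × 0.90 × 0.10 / 0.10² = 34.57.
- All patients: 34.57 / 0.75 = 46.1, which matches 46.
- If W were the full width (half-width 0.05), the result would be 4 × 34.57 / 0.75 = 184.4, which does not match. In the calculation, W acts as a half-width.

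**2. Size of the group behind specificity.** 46 × 0.75 = 34.5, or 50 × 0.9 × 0.75 = 33.75. Expected false positives: 34.5 × 0.10 = 3.45; at 34 patients, 3.4.

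**3. Interval that section 7 implies.** 0.90 ± 1.96 × √(0.09 / 34.5) = 0.90 ± 0.100, so 80.0% to 100.0%.

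**4. Exact coverage of that interval.** With 34 IHC-negative patients and a true specificity of 0.90, the interval lies wholly above 0.90 when 33 or 34 are correctly classified:
- 34 of 34: 0.9³⁴ = 2.8%
- 33 of 34: 34 × 0.9³³ × 0.1 = 10.5%
- together 13.3%; a further 0.5% lie wholly below
- coverage: 100 − 13.3 − 0.5 = 86.2%

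At 35 patients coverage is 87.1%. Averaged over a random IHC-negative count (binomial, 46 and 0.75) it is 87.0%, against 95.2% for Wilson and 97.7% for Clopper-Pearson. Coverage moves up and down with the true value: averaged in the same way, the Wald figure is 91.6% at 0.88, 90.2% at 0.92 and 82.5% at 0.95, so about 82% to 92% between 0.85 and 0.95.

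**5. Interval with adequate coverage.** Wilson at p = 0.90, n = 34.5, z² = 3.84:
- divisor: 1 + 3.84 / 34.5 = 1.111
- centre: (0.90 + 3.84 / 69) / 1.111 = 0.860
- half-width: 1.96 × √(0.09 / 34.5 + 3.84 / (4 × 34.5²)) / 1.111 = 0.103
- limits: 75.7% to 96.3%, so 14.3 points below the estimate and 6.3 above

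| IHC-negative patients | Wald lower limit at 90% | Wilson | Clopper-Pearson lower limit |
|---|---|---|---|
| 30 | 79.3% | 74.4% to 96.5% | 73.5% |
| 34 | 79.9% | 75.6% to 96.3% | 74.8% |
| 35 | 80.1% | 75.8% to 96.3% | 75.1% |
| 38 | 80.5% | 76.5% to 96.1% | 75.9% |

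The last row is close to the case in which all 50 patients are evaluable (50 × 0.75 = 37.5).

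**6. The interval that section 6.1 does plan.** The ICC-positive frequency uses all of about 46 patients. With specificity 90% and an assumed sensitivity of 70% to 100%, the expected frequency runs from 0.25 × 0.70 + 0.75 × 0.10 = 25% to 0.25 × 1.00 + 0.75 × 0.10 = 32.5%. Wald coverage at 25%, 26.25%, 30% and 32.5% is 93.8%, 92.4%, 94.3% and 93.9%; Wilson gives 96.1%, 93.7%, 94.7% and 96.1%. The choice matters little there.

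**The case against.** A reader might infer that the trial will report a Wald interval for specificity and that its nominal 95% interval will therefore cover only about 87% of the time. The documents do not support that. Section 7 uses the normal approximation only to set n, and section 6.1 plans no interval for specificity or sensitivity. Sizing with a closed formula and later reporting a Wilson or exact interval would be consistent with every sentence in the plan. The 87% describes the planning approximation, not a prescribed analysis. It is also one value on an uneven curve, and the plan gives specificity only as approximately 90%.

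Nor does the protocol state a lower limit of 80%; that follows from SP and W once W is read as the half-width that reproduces 46. And this is a pilot: section 2 says it is meant to create hypotheses, section 7 claims only a qualitative assessment of feasibility, and no success threshold is tied to a lower limit.

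All of this stands, and it lowers the weight of the point. It does not remove it. Section 7 does state a 10% interval figure as the basis for its size, and about 34 IHC-negative patients do not deliver it on either reading. As a full width, the interval is about 20 points wide; as a half-width, the lower arm is about 14 points. Relabelling W would cure the first problem but not the second.

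**Conclusion.** The point holds as a minor correction to the stated precision. At an observed specificity of 90%, the planned size supports a 95% interval of about 76% to 96% (Wilson), with a lower limit of about 75% under Clopper-Pearson, instead of the implied 80% to 100%. The shortfall is about 4 to 5 points at the lower limit.

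This assumes 25% prevalence and 45 to 46 evaluable patients, both from section 7. It is not sensitive to them: from 30 to 38 IHC-negative patients the Wilson lower limit stays between 74.4% and 76.5%. The sample size arithmetic itself is reproduced, and nothing here shows that 46 or 50 is too few for a pilot. On the analysis side the fault is an omission: no interval is planned for sensitivity or specificity, and no method is named for the ICC-positive frequency.

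**What to change.** In section 7, keep 46 and 50 patients. Describe W as the half-width used to set n, and add that at an observed specificity of 90% with about 34 IHC-negative patients the expected 95% interval is about 76% to 96%.

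In section 6.1, state that specificity and sensitivity will be reported with 95% Wilson intervals, and use the same method for the ICC-positive frequency. Clopper-Pearson is an equally acceptable choice if coverage of at least 95% is wanted throughout: at exactly 35 IHC-negative patients and a true 90%, Wilson coverage dips to 92.0% while Clopper-Pearson is 98.0%. If it is chosen, quote its lower limit of about 75% in section 7.

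Naming the method matters most for sensitivity, with about 46 × 0.25 = 11.5 IHC-positive patients. If all of 11 are detected, a normal-approximation interval has zero width, whereas the Wilson lower limit is 74%.

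The cost is a sentence in section 6.1 and a restated figure in section 7, with no extra patients or data. The downside is a less favourable stated lower limit, about 76% instead of 80%.

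### The sample-size formula treats W as the half-width of the confidence interval but the plan calls it the width, so 46 patients give an interval about 20 points wide, not 10

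*Combined protocol and SAP*

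**What the plan says.** Section 7 (Sample Size Calculation) bases the sample size on the precision of the specificity of ICC against IHC, using a published method that allows for prevalence. The printed formula is n = [Z² × SP(1 − SP) / W²] / (1 − P). The inputs are a 5% alpha for Z, SP as "specified specificity (90" per cent), P as "prevalence of disease (25" per cent), and W as "width of 95% confidence interval (10" per cent).

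The result is given as "This resulted in a number of 46 patients", "which was amended by a drop-out rate of approx. 10" per cent, for a total of 50.

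The plan does not describe W anywhere as a half-width, a margin or a plus-or-minus figure, and it gives no expected confidence limits for specificity. Section 6.1 promises a 95% confidence interval for the frequency of ICC-positive patients but names none for specificity.

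**The concern.** The width of a confidence interval ordinarily means the upper limit minus the lower limit. Read that way, section 7 promises an interval 10 points wide, for example 85% to 95% around a specificity of 90%. The formula does not deliver that, because its W is the distance to one limit only.

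This matters because a specificity of about 90% is the main hypothesis (sections 2 and 6.1), and this line is the only precision target behind the sample size. A lower limit near 85% and one near 76% support different judgements about whether ICC is good enough. The study is also meant to inform later work: anyone who reused this formula and label to obtain a 10-point-wide interval would plan about a quarter of the patients needed.

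**Working it through.** **Inputs, all from section 7:** z = 1.96 (two-sided alpha 0.05), SP = 0.90, P = 0.25, W = 0.10.

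**1. Reproduce the plan's figure.**
- IHC-negative patients needed: 1.96² × 0.90 × 0.10 / 0.10² = 34.57.
- Total: 34.57 / (1 − 0.25) = 46.10. This matches the stated 46 (47 if rounded up).
- Alternatives do not match: a one-sided z gives 32.5, and dividing by P instead of 1 − P gives 138.3.

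**2. Identify what W is.** Rearranging the formula gives W = z × √[SP(1 − SP) / (n(1 − P))]. This is z times the standard error of the specificity estimate, so it is the half-width of a normal-approximation interval.

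**3. Compute the interval the design gives.** Half-width = 1.96 × √[0.09 / (0.75N)].

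| Analysable N | IHC-negative (0.75N) | Half-width (points) | Full width (points) |
|---|---|---|---|
| 45 (50 less 10%) | 33.75 | 10.1 | 20.2 |
| 46 | 34.5 | 10.0 | 20.0 |
| 50 (no loss) | 37.5 | 9.6 | 19.2 |

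At N = 46 the interval is about 80% to 100%.

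**4. Compute the sample for a true 10-point width.** The half-width is then 0.05:
- 1.96² × 0.09 / 0.05² = 138.3 IHC-negative patients.
- 138.3 / 0.75 = 184.4, so 185 patients before drop-out. Halving W quadruples n.

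**5. Check other interval methods.** The normal approximation is weak at 90% with so few negatives, so the check was repeated from the binomial distribution with 34 IHC-negative patients (34.5 rounded down).
- 31/34 (91.2%): Clopper-Pearson 76.3% to 98.1%, Wilson 77.0% to 97.0%.
- 30/34 (88.2%): Clopper-Pearson 72.5% to 96.7%.
- Expected width at a true specificity of 0.90: 22.1 points (Clopper-Pearson), 20.2 points (Wilson).
- Actual coverage of the normal-approximation (Wald) interval at a true specificity of 0.90: 86.2%, against a nominal 95%.

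Every method gives a width of about 20 points or slightly more.

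**The case against.** The strongest reply is that this is a loose label and not a design fault. Width is sometimes used informally for the distance to one limit, and on that reading formula, inputs and result agree. All of them are printed together, so a careful reader can see how W was used. No analysis, endpoint or decision rule depends on the 10%, the study is a hypothesis-generating pilot, and the plan claims only a qualitative view of feasibility. A later study would also rely on the observed counts and not on this planning label.

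Much of this is fair. The 46 is right for a half-width, the pilot purpose softens the consequence, and the documents do not show which precision was intended. The 185 figure is therefore a shortfall only if a 10-point total width was meant. Two supporting points also need care. The poor Wald coverage concerns planning only, because the plan names no interval method for specificity. And 31/34 is one possible outcome, not the result the study will produce.

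None of this makes the definition true. The plan defines its own symbol, nothing in it signals the informal reading, and on the plain reading the stated precision is one the design does not have. How the cited methods paper defines W was not checked; the conclusion does not need it.

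**Conclusion.** The concern holds. As written, section 7 attributes to the design a 95% interval for specificity that is 10 points wide. The same formula and inputs give about 20 points: 20.0 at 46 patients, 19.2 if all 50 are analysable, and about 22 on average with an exact interval and 34 negatives. The error is a factor of two in the stated precision, equivalent to a factor of four in sample size (46 against 185).

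This rests on the plan's own assumptions of 90% specificity and 25% prevalence, and on reading width as the distance between the two limits. The arithmetic behind 46 is sound; the description of what it achieves is wrong and should be corrected.

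**What to change.** In section 7, redefine W as the half-width of the 95% confidence interval (10 percentage points; full width about 20 points). Add an illustrative exact or Wilson interval, marked as an example: 31 of 34 IHC-negative patients correctly classified gives about 76% to 98% (exact) or 77% to 97% (Wilson). Make no claim to a 10-point-wide interval.

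The sponsor should confirm that plus or minus 10 points was the intended precision. If it was, the change is a one-line correction with the sample size unchanged, and its only cost is a less favourable precision statement. If a 10-point total width was intended, either that target must be dropped or the sample must rise to 185 before drop-out.

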3.2. Secondary Endpoints

- IHC results of different bronchoscopic samples

4. Study Population

The population for selection of potential study participants is comprised of clinical routine patients presenting with (suspected malignant) pleural effusion. These patients must have an indication for pleural puncture. The cause and nature of the pleural effusion (e.g. presence of non-small cell lung cancer, NSCLC) at this time point will be unknown in many cases. To establish this, further routine diagnostic procedures are required. While patients will be included before the planned routine examinations and thus before presence of NSCLC can be confirmed, only patients with confirmed diagnosis of non-small cell lung cancer will be included in the data analysis.

A patient in whom suspicion of pleural manifestation of lung cancer is not confirmed, will be considered a screening failure and thus excluded from the study.

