4.1. Inclusion Criteria

- Age \geq 18 years
- Presence of malignant pleural effusion with indication for pleural puncture and thoracoscopy
- Confirmed diagnosis of non-small cell lung cancer according to ERS guidelines (to be confirmed after study inclusion when results from routine clinical examinations are available)
- Written informed consent

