5.1. Selection of Patients

Patients presenting within clinical routine with pleural effusion and suspected or known underlying lung cancer and who satisfy the in- and exclusion criteria as far as they can be assessed at that time, are considered for study participation.

These patients will be informed about all routine clinical examinations and assessments before informed consent will be obtained. However, informed consent for study participation will be obtained before (routine) pleural puncture to ensure that patients agree with the study-specific additional diagnostic analysis of the collected pleural effusion material.

All invasive procedures described herein are part of the patient's clinical routine treatment to achieve a clinical diagnosis. The routine examinations and study-associated data collection for each patient are outlined below. The individual patient's study participation will be concluded, once all of these steps are completed.

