5.5. Optional bronchoscopic lung biopsy (non-study specific routine examination)

In some cases, suspicious tumor masses within the lung and/or intrathoracic lymph nodes are detected by preceding radiologic assessment and routinely sampled for further histological analyses. This applies in particular when no histological samples can be obtained from the pleura. In these cases, the corresponding results will also be considered for study-associated analysis.

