5.6. Immunocytochemistry (ICC) and Immunohistochemistry (IHC)

The pleural fluid obtained by pleural puncture will be in part used for standard clinical routine analysis and another part will be subject to study-specific PD-L1 analysis. The same applies to the histological samples obtained by thoracoscopy and potential bronchoscopy. These analyses will reveal nature and cause of the pleural effusion. In case the corresponding results confirm an NSCLC diagnosis, all results from ICC and IHC will be collected for analysis within the study. Should the results rule out NSCLC, the patient will be considered a screening failure and excluded from the study.

For PD-L1 analysis in both ICC and IHC, the PD-L1 IHC 22C3 pharmDx Kit (Dako) will be used.

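### Does n=50 in Section 7 count every patient included before diagnosis, or only patients with confirmed NSCLC?

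*Combined protocol and SAP*

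**What the plan says.** Section 7 sizes the study on the precision of specificity. It reaches 46 patients, "which was amended by a drop-out rate of approx. 10% to give a total patient number of" 50. Drop-out is not defined there and screening failures are not mentioned.

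Other sections describe the order of events:

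- Section 4 states that "patients will be included before the planned routine examinations and thus before presence of NSCLC can be confirmed", and limits the analysis to confirmed NSCLC. A patient whose suspected pleural lung cancer is not confirmed "will be considered a screening failure and thus excluded from the study".
- Section 4.1 lists confirmed NSCLC as an inclusion criterion, "to be confirmed after study inclusion when results from routine clinical examinations are available".
- Section 4.2 makes the ruling-out of NSCLC by the routine work-up an exclusion criterion.
- Section 5.1 draws on patients with "suspected or known underlying lung cancer".
- Section 5.6 repeats the rule: "Should the results rule out NSCLC, the patient will be considered a screening failure and excluded from the study".

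The text available gives no rule on replacing screening failures and no expected confirmation rate.

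**The concern.** Because inclusion comes before diagnosis, a total patient number can be read as a count of inclusions. Some of the 50 would then be removed once NSCLC is ruled out, and the margin of 4 patients between 46 and 50 would have to absorb them as well as ordinary drop-outs. The alternative is that 50 counts confirmed patients and screening failures fall outside it. Section 7 does not choose between the two in so many words.

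The choice would set when recruitment stops and how many IHC-negative patients inform specificity, which is the quantity the study was sized for.

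A related question is whether a patient with only bronchoscopic histology counts toward the 46. Section 5.5 says of bronchoscopic sampling: "This applies in particular when no histological samples can be obtained from the pleura".

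**Working it through.** **Inputs (Section 7).** z = 1.96 for a two-sided 95% interval; SP = 0.90; W = 0.10; P = 0.25. W is labelled a width but enters the formula as a half-width, and I use it as the formula does. That label is a separate matter from the counting unit.

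**The plan's own figure.** n = [z² × SP(1−SP) / W²] / (1−P) = [3.8416 × 0.09 / 0.01] / 0.75 = 34.57 / 0.75 = 46.10, stated as 46. Expected IHC-negative patients: 0.75 × 46 = 34.5.

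**The step to 50.** 46 × 1.1 = 50.6 and 46 / 0.9 = 51.1, so 50 fits an allowance of about 10%. Exactly, it covers 50 − 46 = 4 losses, or 4/50 = 8%.

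**Half-width for N analysable patients.** h = 1.96 × √(0.09 / (0.75 × N)). At N = 46, h = 10.0 points.

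**Reading B: 50 confirmed patients.** With no loss, N = 50 and h = 9.6 points. With 10% loss, N = 45 and h = 10.1 points. The confirmation rate affects only the number of consents needed.

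**Reading A: 50 inclusions before diagnosis.** Reaching 46 requires 46/50 = 92% confirmed and nobody else lost. The confirmation rates c below are my assumptions.

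| c | A: analysable (50c) | A: IHC-negative | A: half-width, no other loss | A: half-width, with 10% drop-out | B: inclusions for 50 confirmed (50/c) |
|---|---|---|---|---|---|
| 90% | 45 | 33.8 | 10.1 points | 10.7 points | 56 |
| 70% | 35 | 26.3 | 11.5 points | 12.1 points | 72 |
| 50% | 25 | 18.8 | 13.6 points | 14.3 points | 100 |

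**Which reading the text supports.**

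1. The 25% in Section 7 is a prevalence of PD-L1 positivity in NSCLC patients. Multiplying by 1 − P gives IHC-negative patients only if the 46 are NSCLC patients.
2. The allowance added to the 46 is for drop-out. The plan has a different term, screening failure, for patients without confirmed NSCLC, and Sections 4 and 5.6 put them outside the study. Section 4.2 does the same through an exclusion criterion.
3. Adding drop-outs to 46 NSCLC patients gives a total that is still made up of NSCLC patients.

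These steps lead to Reading B. The use of included for a patient who may later be a screening failure is loose, but Section 4 explains the sequence openly and Sections 4.1, 4.2, 5.1 and 5.6 follow it. It is not a contradiction.

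**Bronchoscopic histology.** Section 3.1 ties the primary IHC outcome to pleural biopsy, and Section 3.2 makes bronchoscopic IHC a secondary endpoint. A patient with bronchoscopic histology only therefore falls naturally under the secondary endpoint. Section 5.5, which lets those results be considered in the study's analysis, is compatible with this.

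**The case for a change.** The best case for a change runs as follows. An inflation step normally turns an analysable number into an enrolled number, and in this plan enrolment precedes diagnosis. The NSCLC prevalence therefore fixes what the 46 are but does not strictly fix what the 50 are. Section 4 concedes that the cause of the effusion will often be unknown at inclusion, so a confirmation rate of 92% cannot be presumed. A study sized on precision should say when recruitment ends, and saying so would cost one sentence. Counting confirmed patients would add consents and PD-L1 analyses but no invasive procedures, since Section 5.1 makes these routine care.

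Part of this stands. Section 7 lacks the sentence, and someone reading it in isolation could take 50 as a consent target. Nothing in the documents shows that the confirmation rate is high: a malignant effusion need not come from NSCLC.

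It does not carry further. The reading that produces a shortfall needs screening failures to be counted as drop-outs, although the plan names them separately and removes them from the study. The size of any shortfall rests wholly on a rate the documents do not give. Stopping at 50 inclusions would also not be hidden, because Section 6.1 requires the positive and negative counts for each sample type.

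**Conclusion.** The observation is correct but no change to the plan follows. Section 7 leaves its counting unit unstated, and a reader who takes it together with Sections 4, 4.2 and 5.6 fills the gap sensibly: 50 means patients with confirmed NSCLC. On that reading screening failures cause no shortfall, and the expected half-width is 9.6 to 10.1 points, against 10.0 at the planned 46. The less likely reading would give 10.1 to 13.6 points over assumed confirmation rates of 90% down to 50% with no other loss, or 10.7 to 14.3 points with 10% drop-out as well.

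Section 2 calls this a pilot to create hypotheses. Section 7 claims at least a qualitative assessment of feasibility and a basis for later studies. No success threshold is tied to the interval, so writing down the counting unit would change no decision rule and, on the likelier reading, no figure.

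The conclusion rests on taking W as a half-width, as the formula does, and on the text available containing no other statement of what the 50 count. It does not certify 46 and 50 in any other respect.
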